10.5 Compliance

Interferon Alpha-2b, Rintatolimod and the morning dose of Celecoxib will be administered in the Clinical Research Center (or other clinical area) and documented by the nurse on the Medication Administration Record. The evening dose of Celecoxib will be self-administered at home and documented by the participant on the patient diary. The participant will be asked to bring the diary with him/her to each clinical visit. Refer to Appendix H

PROTOCOL TITLE: Phase 2A Study Evaluating a Chemokine-Modulatory Regimen in Patients with Colorectal Cancer Metastatic to the Liver

11 PROCEDURES INVOLVED

11.1 Description of Procedures

The study-specific assessments are detailed in this section and outlined in Appendix F (Study Calendar). Baseline and/or Screening assessments must be performed within 14 days prior to the first dose of investigational product unless otherwise noted. Any results falling outside of the reference ranges may be repeated at the discretion of the investigator. All on-study visit procedures are allowed **a window of ± 1 day** unless otherwise noted.

Unless otherwise defined in the written protocol text, all procedures/assessments will be conducted in accordance with RPCI Clinical Research Services Standard Operating Procedures.

Informed consent **MUST** be completed prior to receiving any study related procedures.

11.1.1 Screening (performed between days -14 through day -1 unless otherwise specified)

- Recording of concomitant medications
- Medical and Surgical History
- Complete Physical Exam including height and weight
- Vital Signs
- ECOG Performance Status Assessment
- Hematology
- Chemistry
- CEA Level
- ANA testing
- Serum HCG pregnancy testing (within 7 days of Day 1 in women of child-bearing potential only)
- CT and/or MRI (within 28 days of start of treatment)
- EKG
- Liver Biopsy

11.1.2 Evaluations Performed on day 1 of each treatment week (day 1, 8, 15):

- Recording of concomitant medications
- Recording of Adverse Events
- Targeted Physical Exam including weight
- Vital Signs (temperature, blood pressure, pulse rate and respiratory rate) will be performed pre- treatment and at 30 and 60 minutes post rintatolimod
(± 5 minutes).
- ECOG Performance Status Assessment
- Hematology
- Chemistry
- Chemokine Modulating regimen
- Blood (60cc) for correlative studies on Day 1 and Day 15 only (within 1 hour after end of infusion treatment)

PROTOCOL TITLE: Phase 2A Study Evaluating a Chemokine-Modulatory Regimen in Patients with Colorectal Cancer Metastatic to the Liver

11.1.3 Evaluations Performed on days 2 and 3 of each treatment week(days 2,3, 9, 10, 16, 17):

- Recording of concomitant medications
- Recording of Adverse Events
- Vital Signs (temperature, blood pressure, pulse rate and respiratory rate) will be performed pre-treatment and at 30 and 60 minutes post rintatolimod (\pm 5 minutes).
- Chemokine Modulating regimen
- Blood (60cc) for correlative studies on Day 3 only (within 1 hour after end of infusion treatment)

11.1.4 Evaluations Performed on Day 20 (+/- 2 days):

- Recording of Adverse Events
- Liver Biopsy

11.1.5 End of Treatment Visit on Day 29 (+/- 10 days):

- Recording of concomitant medications
- Recording of Adverse Events
- Targeted Physical Exam including weight
- Vital Signs
- ECOG Performance Status
- Hematology
- Chemistry

NOTE: In the event patient cannot tolerate treatment with all 9 days of treatment, then Blood 60cc for correlative will be collected at time that the patient recovers from toxicities (ideally within 1 week of the last infusion). Liver biopsy will also be collected provided there is not an overriding safety concern for the patient.

11.1.6 Follow-up (patients will be followed for 12 months after EOT visit)

- Survival status (phone contact/chart review is acceptable)
- CT scan and/or MRI: to be performed at day 46 (\pm 3 days). If reassessment scan shows stable disease/response, patients will continue in follow-up with CT imaging every 8 weeks until progression, clinical deterioration or withdrawal from study. If in the clinical judgment of the treating team, it is in the best interest of the patient to pursue another therapeutic option, the patient will come off study and CT imaging will be obtained only as SOC/protocol. In this instance, review of the subsequent disease assessment study will be requested for determination of RECIST parameters.

11.2 Correlative studies (blood samples)

Five (10 mL) green-top heparinized tubes of blood will be collected via venipuncture for biomarker analysis at multiple time points. These will be collected as outlined in section 11.1. All tubes will be sent to the RPCI Hematologic Procurement Shared Resource Laboratory.

PROTOCOL TITLE: Phase 2A Study Evaluating a Chemokine-Modulatory Regimen in Patients with Colorectal Cancer Metastatic to the Liver

Hematologic Procurement Shared Resource
Attn: I 52917 Specimens
[name]
[name]
[name]
[contact]

In addition 1 (10 mL) green-top heparinized tube will be sent to [name] in [name] to the attention of [name] contact [contact] or cell [contact]. This will be for preliminary analyses, which may include the pre- and post-treatment cytokine levels and immune cell subsets, via RT-PCR, flow cytometry assays, or alternative laboratory methods.

NOTE: All six tubes will be sent to RPCI Hematologic Procurement Shared Resource Laboratory first for sample tracking. The Procurement Shared Resource will then forward 1 (10mL0 green-top to [name]

Plasma samples are to be processed at 4°C using a refrigerated centrifuge at approximately 3000 rpm for about 10 minutes with the plasma being aliquoted into 2 cryovials per time-point. The samples will immediately be frozen at -70°C or below until analyzed. PBMC's will then be obtained by Ficoll gradient as per the lab's standard procedure. Two of the tubes will be pooled and the PBMC's will be frozen in Gibco Cell culture freezing media and will be stored in LN2 until time of analysis. The remaining tube of PBMC's will be frozen in RNA later and will be stored in -70 degrees or below until analyzed. The screw cap polypropylene cryogenic tubes will be labeled with the clinical study number, participant's MR number, participant's study number, protocol time point, protocol day, date and time of draw.

As a component of exploratory aims, blood may be analyzed to assess pre- and post-treatment cytokine levels and immune cell subsets, via ELISA, RT-PCR and flow cytometry assays.

Note: All investigator or analyzing research laboratories housing research samples need to maintain current **Temperature Logs** and study-specific **Sample Tracking and Shipping Logs**. The Principal Investigator/Laboratory Manager **must** ensure that the stated lab(s) have a process in place to document the receipt/processing/storage/shipping of study-related samples/specimens. This is required for both observational and interventional clinical studies collecting clinical samples.

11.3 Pathology

Fresh Biopsy Samples

At each liver biopsy collection time point, 6 total cores will be obtained, including at least 5 tumor cores and 1 additional core of surrounding liver tissue (to enhance the stringency of our assays). 4 cores of tumor and 1 core of surrounding liver tissue will be placed in Dulbecco's Phosphate-Buffered saline, and 1 core of tumor will be placed in formalin, and processed to FFPE block per institute standard.

Pre- and post-treatment cores should be obtained from the same lesion. If non-necrotic lesions are present at baseline, they should be prioritized for biopsy, with the necrotic lesions being

PROTOCOL TITLE: Phase 2A Study Evaluating a Chemokine-Modulatory Regimen in Patients with Colorectal Cancer Metastatic to the Liver

avoided per the interventional radiologists' discretion. Any biopsy core which appears as necrotic should be discarded.

Label the samples with study-specific subject ID number, clinical study number, protocol time point and, protocol day. Phosphate-Buffered saline, will be supplied by [name] lab and sample will be kept at ambient temperature. Samples in Dulbecco's Phosphate-Buffered Saline will be sent to [name] lab upon completion of processing (preferably ASAP within 2 hours of collection, but within 4 hours of collection is allowed). Once the remaining core has been processed to FFPE block, it will be delivered to OmniSeq

- The changes in the ratio between CTL marker (CD8a gene expression) to Treg markers (FoxP3 gene expression), using RT-PCT will be considered as a primary endpoint of efficacy.

Additional correlative studies may be performed on the same material:

- Comparison (using RT-PCR, Immunofluorescence [IF] and immunohistochemistry [IHC] on serial sections) of the metastatic tissue specimen with regard to total numbers of infiltrating T cells, their CD4/CD8 ratios, frequencies of FoxP3 cells, and the expression of chemokine receptors on CD4⁺ and CD8⁺ T cells (CXCR3, CCR5, CCR4, CCR6, and CXCR4).
- Evaluate the local expression of T_{eff}-attracting chemokines (CCR5, CXCL9, CXCL10 and CXCL11) and T_{reg}-favoring chemokines (CCL22 and CXCL12) using IF and RT-PCR.
- Additional tissue evaluations, including OmniSeq Immune Report card, NanoString or similar, may be performed, depending on the availability of funding.

12 WITHDRAWAL OF SUBJECTS

12.1 Treatment Discontinuation

Upon treatment discontinuation all end of treatment evaluations and tests will be conducted. All participants who discontinue due to an AE must be followed until the event resolves or stabilizes. Appropriate medical care should be provided until signs and symptoms have abated, stabilized, or until abnormal laboratory findings have returned to acceptable or pre-study limits. The final status of the AE will be reported in the participant's medical records and the appropriate eCRF.

Reasons for treatment discontinuation should be classified as follows:

- Death
- Progressive disease
- Toxicity; treatment related or unrelated
- Investigator judgment
 - The Investigator may discontinue a participant if, in his/her judgment, it is in the best interest of the participant to do so.
- Noncompliance
- Participant voluntary withdrawal

PROTOCOL TITLE: Phase 2A Study Evaluating a Chemokine-Modulatory Regimen in Patients with Colorectal Cancer Metastatic to the Liver

- A participant may withdraw from the study at any time, for any reason. If a participant discontinues treatment, an attempt should be made to obtain information regarding the reason for withdrawal.
- Sponsor decision.

13 RISKS TO SUBJECTS

13.1 Celecoxib

Prolonged use of celecoxib may cause dyspepsia, headaches (including migraines) and borderline elevated liver function tests (which could indicate liver damage). Recently, information from three long-term studies of celecoxib has become available. In the first study, a cancer prevention study, an increased risk of heart attacks, strokes, and/or deaths resulting from heart or blood vessel disease was reported among people taking celecoxib. Approximately 1 in 100 subjects enrolled in this study receiving the placebo treatment had one of these serious events. In contrast, between 2 and 3 in 100 subjects taking celecoxib (between 400 and 800 mg daily) had one of these serious events. Another clinical cancer prevention study found no increased risks in subjects taking celecoxib 400 mg daily. The third study, an Alzheimer's disease prevention study, did not find increased risks with celecoxib. Dosing has been suspended in all three of these studies based on the findings of the first cancer prevention study. As a result, the FDA is now evaluating the possibility that celecoxib increases the risk of heart attack, stroke, and or death resulting from heart or blood vessel disease. Known infrequent side effects of celecoxib include nausea and/or vomiting, diarrhea, flatulence, abdominal and stomach pain, bleeding ulcer, upper respiratory tract infection, pharyngitis, rhinitis, sinusitis, peripheral edema, back pain, dizziness, insomnia, and skin rash. Rare risks include sudden death (unexpected or instant death that occurs within minutes or hours from any cause other than violence), vasculitis, hepatitis, liver failure, kidney failure, blood dyscrasias, hypoglycemia, hyponatremia, viral meningitis, severe allergic reaction, visual changes, and transient ischemic attack. **Warnings/Precautions:** Stomach problems may be more likely to occur if patients drink alcoholic beverages while taking this medicine. Taking two or more of the nonsteroidal anti-inflammatory drugs together on a regular basis may increase the chance of unwanted effects. Also, taking acetaminophen, aspirin or other salicylates, or ketorolac (e.g., Toradol) regularly, while taking a nonsteroidal anti-inflammatory drug, may increase the chance of unwanted effects. The risk will depend on how much of each medicine is taken every day and how long the medicines are taken together. Therefore, patients should not take acetaminophen or aspirin or other salicylates or ketorolac (e.g., Toradol). Clinical studies with celecoxib have identified potentially significant interactions with fluconazole and lithium. Experience with nonsteroidal anti-inflammatory drugs (NSAIDs) suggests the potential for interactions with furosemide and ACE inhibitors. Celecoxib is contraindicated in patients with known hypersensitivity to celecoxib. Celecoxib should not be given to patients who have demonstrated allergic-type reactions to sulfonamides. Celecoxib should not be given to patients who have experienced asthma, urticaria, or allergic-type reactions after taking aspirin or other NSAIDs. Severe, rarely fatal, anaphylactic-like reactions to NSAIDs have been reported in such patients.

For more risk information reference the Investigator's Brochure or package insert.

PROTOCOL TITLE: Phase 2A Study Evaluating a Chemokine-Modulatory Regimen in Patients with Colorectal Cancer Metastatic to the Liver

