3.2 Exclusion criteria

Participants will be excluded from the study for the following:

1. Patients currently treated with systemic immunosuppressive agents, including steroids, are ineligible until 3 weeks after removal from immunosuppressive treatment.
2. Patients with active autoimmune disease requiring ongoing immunosuppressive therapy or, history of transplantation.
3. Patients who are pregnant or nursing. Women of childbearing potential (WOCBP) will have to undergo a urine pregnancy test as part of screening.
4. Untreated CNS metastases.
5. Cardiac risk factors including:
 - Patients experiencing cardiac event(s) (acute coronary syndrome, myocardial infarction, or ischemia) within 3 months of signing consent
 - Patients with a New York Heart Association classification of III or IV (Appendix A)
6. History of upper gastrointestinal ulceration, upper gastrointestinal bleeding, or upper gastrointestinal perforation within the past 3 years. Patients with ulceration, bleeding or perforation in the lower bowel are not excluded.
7. Prior allergic reaction or hypersensitivity to celecoxib, NSAIDs, or any study agents which would prevent completion of protocol-therapy.
8. Patients are ineligible if they plan on regular use of NSAIDs at any dose more than 2 times per week (on average) or aspirin at more than 325 mg at least three times per week, on average. Low-dose aspirin not exceeding 100 mg/day is permitted. Patients who agree to stop regular NSAIDs or higher dose aspirin are eligible and no wash out period is required.
9. Received an investigational agent within 30 days prior to enrollment.
10. Unwilling or unable to follow protocol requirements.
11. Patients with known serious mood disorders.
12. Any additional condition which in the Investigator's opinion deems the participant an unsuitable candidate to receive the study drugs

Please refer to Appendix E for the Investigator Study Eligibility Verification Form: Exclusion Criteria.

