10 TREATMENT

10.1 Dosing and Administration

10.1.1 Chemokine modulating regimen

For dosing, refer to Table 1. The chemokine modulating regimen will be administered on an outpatient basis at Roswell Park Cancer Institute over 3 consecutive days, every week x 3 weeks (Days 1, 2, 3, 8, 9, 10, 15, 16, 17) in the following order:

- Pretreatment: 500 mL Normal saline IV over 60 minutes
- Pre-meds: Acetaminophen (Tylenol) 650 mg by mouth x 1 dose; Prochlorperazine (Compazine) 10 mg by mouth x 1 dose – administered 30 minutes (\pm 5 minutes) after starting pre-treatment hydration

PROTOCOL TITLE: Phase 2A Study Evaluating a Chemokine-Modulatory Regimen in Patients with Colorectal Cancer Metastatic to the Liver

- Celecoxib: 200 mg orally, administered along with pre-meds
- Interferon Alpha-2b : (20 million units/M²) IV over 20 minutes
- Rintatolimod: 200 mg IV, initial administration should begin at a slow rate of infusion (approximately 20 cc/ hour) and increase to 40 cc/ hour after 30 minutes. Tubing should be flushed with 30 to 50 mL of normal saline solution upon completion. Administration will be followed by 1 hour of observation and vital signs at 30 and 60 minutes post infusion (\pm 5 minutes)
- Celecoxib: 200 mg orally to be taken by the patient at home approximately 12 hours following the initial dose.

Pretreatment and pre-meds listed above are recommendations and may be modified based upon institutional SOC requirements and at the discretion of the investigator. Treatment is intended for an outpatient setting. However, at the investigator's/physician's discretion, the participant may receive treatment as an inpatient, if deemed necessary.

Each 3 day treatment will be initiated after interval history and physical examination is performed and once the relevant laboratory studies have been confirmed to be within clinically acceptable ranges, specifically: ANC \geq 1000/mm³, total bilirubin \leq 1.5 x ULN or \leq 3 x ULN (for patients with Gilbert's Syndrome), AST and ALT $<$ 3 x ULN (or $<$ 150% of values at baseline). Treatment may be delayed up to 3 weeks to allow for resolution of any intercurrent illness or for logistical reasons. Delays beyond 3 weeks will require discussion with the study PI to review appropriateness of continuing therapy on study.

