10.2.1 Celecoxib Non-Hematologic Toxicities

Considered to be possibly, probably, or definitely related to Celecoxib (Interferon Alpha-2b and rintatolimod will be continued). See Table 2. Celecoxib will be discontinued for any attributable grade ≥ 2 toxicity, except for nausea, vomiting, or a similar readily manageable condition.

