Caution: Subjects who had a mild to moderate hypersensitivity reaction have been successfully re-challenged, but careful attention to prophylaxis and bedside monitoring of vital signs is recommended. Hypersensitivity reactions to Interferon Alpha-2b and/or rintatolimod will be managed as follows:

- Mild symptoms (e.g., mild flushing, rash, pruritus): Complete infusion. Supervise at bedside. No treatment required.

PROTOCOL TITLE: Phase 2A Study Evaluating a Chemokine-Modulatory Regimen in Patients with Colorectal Cancer Metastatic to the Liver

- Moderate symptoms (e.g., moderate rash, flushing, mild dyspnea, chest discomfort): Stop infusion. Give intravenous diphenhydramine 25 mg and intravenous dexamethasone 10 mg. Resume infusion after recovery of symptoms at a low rate, then, if no further symptoms, at full dose rate until infusion is complete. If symptoms recur, stop infusion. The subject should receive no additional Interferon Alpha-2b or rintatolimod for that week's three-day treatment, but may be retreated after discussion with the investigator. Record toxicity.
- Severe life threatening symptoms (e.g., hypotension requiring pressor therapy, angioedema, respiratory distress requiring bronchodilation therapy, generalized urticaria): Stop infusion. Give intravenous diphenhydramine and dexamethasone as above. Add epinephrine or bronchodilators if indicated. If wheezing is present, that is not responsive to bronchodilators, epinephrine is recommended. Subject should be removed from further protocol therapy. Report as serious adverse event.

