32.1 Celecoxib

A sulfa non-steroidal anti-inflammatory drug (NSAID) used in the treatment of osteoarthritis, rheumatoid arthritis, acute pain, painful menstruation and menstrual symptoms, and to reduce numbers of colon and rectum polyps in patients with familial adenomatous polyposis.

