Appendix E

INVESTIGATOR STUDY ELIGIBILITY VERIFICATION FORM: EXCLUSION CRITERIA

Participant Name: _____

Medical Record No. : _____

Title: Phase 2A Study Evaluating a Chemokine-Modulatory Regimen in Patients with Colorectal Cancer Metastatic to the Liver

EXCLUSION CRITERIA				
Yes	No	N/A	All answers must be "No" or "N/A" for participant enrollment.	Date
			1. Patients currently treated with systemic immunosuppressive agents, including steroids, are ineligible until 3 weeks after removal from immunosuppressive treatment.	
			2. Patients with active autoimmune disease, requiring ongoing immunosuppressive therapy or history of transplantation.	
			3. Patients who are pregnant or nursing. Women of childbearing potential (WOCBP) will have to undergo a urine pregnancy test as part of screening.	
			4. Untreated CNS metastases	
			5. Cardiac risk factors including: 
○ Patients experiencing cardiac event(s) (acute coronary syndrome, myocardial infarction, or ischemia) within 3 months of signing consent○ Patients with a New York Heart Association classification of III or IV (Appendix A)	
			6. History of upper gastrointestinal ulceration, upper gastrointestinal bleeding, or upper gastrointestinal perforation within the past 3 years. Patients with ulceration, bleeding or perforation in the lower bowel are not excluded.	
			7. Prior allergic reaction or hypersensitivity to celecoxib ,NSAIDs, or any study agents which would prevent completion of protocol-therapy.	
			8. Patients are ineligible if they plan on regular use of	

PROTOCOL TITLE: Phase 2A Study Evaluating a Chemokine-Modulatory Regimen in Patients with Colorectal Cancer Metastatic to the Liver

EXCLUSION CRITERIA				
Yes	No	N/A	All answers must be "No" or "N/A" for participant enrollment.	Date

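### Section 13.1 bars celecoxib after a sulfonamide reaction, but exclusion 7 and Appendix E item 7 do not ask about one

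*Combined protocol and SAP*

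**What the plan says.** Section 13.1 gives three allergy restrictions for celecoxib. It is contraindicated in known hypersensitivity to the drug; "Celecoxib should not be given to patients who have demonstrated allergic-type reactions to sulfonamides"; and it is not to be given to patients who have reacted to aspirin or other NSAIDs with asthma, urticaria or allergic-type symptoms. Section 32.1 introduces celecoxib as "A sulfa non-steroidal anti-inflammatory drug (NSAID) used in the treatment of osteoarthritis", among other uses.

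The allergy criterion is exclusion 7 in Section 3.2: "Prior allergic reaction or hypersensitivity to celecoxib, NSAIDs, or any study agents which would prevent completion of protocol-therapy". The Appendix E verification form repeats it as item 7 with the same limits, ending "or any study agents which would prevent completion of protocol-therapy". Exclusion 12, also on the form, covers any further condition that in the investigator's "opinion deems the participant an unsuitable candidate to receive the study drugs".

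Celecoxib is part of the regimen for every participant: 200 mg twice a day on nine treatment days (Table 1, Sections 10.1.1 and 32.1.4). The morning dose is given in clinic. The other is described as "Celecoxib: 200 mg orally to be taken by the patient at home approximately 12 hours following the initial dose".

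**The concern.** Eligibility is decided on the Section 3.2 criteria and the Appendix E form that the investigator signs. Section 13.1 is a risk description, which nobody has to work through at sign-off. When a restriction stands in the risk section but not on the form, the form can clear a patient for a drug that the protocol says the patient should not receive.

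What is at stake is patient safety and the protocol's agreement with itself. Section 13.1 lists severe allergic reaction among the rare risks of celecoxib. The patient concerned, with a past sulfonamide reaction and no previous celecoxib, is the one a screening question should find before the first dose.

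**Working it through.** The plan has no figure to reproduce here. The check sets each restriction in Section 13.1 against the eligibility text.

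| Section 13.1 restriction | Exclusion 7 / Appendix E item 7 | Elsewhere in the criteria, forms or calendar |
|---|---|---|
| Known hypersensitivity to celecoxib | Named | Not needed |
| Allergic-type reaction to sulfonamides | Not named | No named entry; only the general exclusion 12 |
| Reaction to aspirin or other NSAIDs | Covered by the word NSAIDs | Not needed |

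The last column rests on inclusion criteria 1 to 11, exclusion criteria 1 to 12, Appendices D and E, the screening list in Section 11.1.1 and the study calendar in Appendix F. None of them mentions sulfonamides or sulfa drugs. The only other reference is the drug-class description in Section 32.1.

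Could the present wording of exclusion 7 be read to cover the case?

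1. A sulfonamide antibiotic is not celecoxib, not an NSAID and not a study agent, so on its plain words the criterion does not reach a reaction to one.
2. A class argument (celecoxib is a sulfa drug, so a sulfonamide reaction counts as hypersensitivity to a study agent) does not fit Section 13.1, which lists celecoxib hypersensitivity and sulfonamide reactions as separate restrictions.
3. The investigator can therefore answer No to item 7 truthfully, and No is the answer that permits enrollment.

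Planned celecoxib exposure of a patient cleared this way: 3 days x 3 weeks = 9 days; 2 doses x 9 days = 18 doses; 18 x 200 mg = 3,600 mg. Nine of the 18 doses are taken at home.

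**The case against.** The best reply is that the rule exists and only a prompt is missing. Section 13.1 is current protocol text, and Section 30 requires conduct in line with the protocol. Screening includes a medical history. Exclusion 12 and its line on the form ask whether the patient is unsuitable for the study drugs, and a patient who should not be given celecoxib is a natural case for that answer. A careful investigator would probably exclude the patient. This stands as a partial safeguard. It does not close the gap, because exclusion 12 depends on opinion and on recalling a sentence in another section, whereas the parallel NSAID restriction was given a named criterion.

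Three stronger readings are tempting, and the documents do not support them.

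- A reader might infer that the protocol has no plan for a celecoxib reaction beyond stopping the drug. The stepwise scheme in Section 10.2.3 is indeed limited: "Hypersensitivity reactions to Interferon Alpha-2b and/or rintatolimod will be managed as follows". But Section 10.2 calls for appropriate medical treatment of any adverse effect, and the general row of its Table 2 tells the investigator to hold celecoxib for intolerable grade 2 or grade 3 events and to discontinue it permanently at grade 4.
- A reader might infer that exposure is largely unobserved. The first dose of each treatment day is given in clinic, 30 minutes into a 60-minute hydration. Then come interferon (20 minutes), rintatolimod and one hour of observation. For the 80 mL in Section 32.3.2, 30 minutes at 20 mL/h delivers 10 mL, and the other 70 mL at 40 mL/h takes 105 minutes, 135 minutes in all. The time in clinic after that dose is about 30 + 20 + 135 + 60 = 245 minutes, if the recommended pretreatment is used and nothing is delayed.
- A reader might infer that the gap biases the primary analysis by letting in patients treated with two drugs. Section 10.2.1 already allows this for toxicity: "Considered to be possibly, probably, or definitely related to Celecoxib (Interferon Alpha-2b and rintatolimod will be continued"). Such patients stay evaluable under Section 19.2 if both TIL measurements exist. This is a general feature of the plan that the fix would not remove.

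**Conclusion.** The point holds as a mismatch between the eligibility form and a safety rule that the protocol itself states. One of the three allergy restrictions in Section 13.1 has no named criterion, and a patient allergic only to a sulfonamide is caught only through investigator discretion.

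The gap is narrow. It concerns patients with that history and no known reaction to celecoxib or NSAIDs, and medical history with exclusion 12 may well find them. A reader might want a probability that such a patient is enrolled, or a loss of power. The documents give no prevalence, no allergic risk and no treatment effect without celecoxib, so either figure would rest on invented inputs. Nothing here touches the sample size, the primary test or the safety stopping rule.

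The conclusion assumes that exclusion 7 means what its words say and that the Section 13.1 sentence is meant as an instruction. No passage says that the omission was deliberate.

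**What to change.** In exclusion 7 and in Appendix E item 7, keep the present text and add a separate limb: *or prior allergic-type reaction to sulfonamides*. Place it after a semicolon at the end, or as item 7b, so that the existing clause about preventing completion of therapy does not qualify it. Inserting the word into the middle of the present list would be weaker. If that clause governs the whole list, the investigator would still have to judge whether a sulfonamide reaction prevents completion, while Section 13.1 sets no such condition.

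The cost is a minor amendment to one criterion and one form line, with written IRB approval before use under Section 18.3. It formally excludes the few patients whom Section 13.1 already bars from celecoxib, which every participant is assigned. Dosing, sample size and analysis do not change.
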